The diagnosis of Parkinson's disease will be confirmed by exam or chart review by a movement disorders neurologist prior to study enrollment. A recent office visit (within 3 months) may be used to replace a portion of the screening visit if information needed for determining eligibility is present within the electronic medical record. Upon confirmation of eligibility, subject returns for assessments and procedures as described below.

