7.1 Demographic and Baseline Assessments

7.1.1 Visit 1: Screening

The following procedures will be performed at this visit:

- Obtain written informed consent from study partner and subject (or subject's legally authorized representative) prior to any study related procedures.
- Administer MoCA

- Review Inclusion/Exclusion Criteria.
- Review medical history, as it pertains to inclusion/exclusion criteria, such as research diagnosis, disease severity, and course of PD
- Obtain subject's demographic information (date of birth, gender, race, education, etc.).
- Obtain details of medications taken over the course of the last 30 days
- Complete physical exam, including neurological exam with UPDRS part III. Collect vital signs, height and weight prior to ECG and blood draw.
- Obtain laboratory studies
- Perform a standard 12-lead ECG.
- Study Drug administration training, including Study Drug Diary Training
- Hypoglycemia rescue training
- Visit 2 will be scheduled within 2 weeks (\pm 5 days).

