7.1.2 Visit 2: Baseline/Initial Treatment Visit (Week 0)-fasting

The following procedures will be performed at this visit:

- Review Inclusion/Exclusion Criteria.
- Collect vital signs, orthostatic vital signs and weight.
- Collect concomitant medication information and record AEs/SAEs.
- Neuropsychological testing, including scales for mood, apathy and suicidality assessment (7.5)
- Perform UPDRS III
- Obtain laboratory studies, blood draw and glucose finger sticks
- Study Drug administration training (following cognitive testing).
- Hypoglycemia rescue training.
- Randomization of subject
- Administer first intranasal dose in clinic and provide study kit
- Visit 3 will be scheduled in 21 days (\pm 5 days).

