7.4 PD Motor Assessment

The **United Parkinson's Disease Rating Scale (UPDRS)** is the most widely used clinical rating scale for Parkinson's disease. In this study, we only use part III of the rating scale, which is a clinician-scored monitored motor evaluation, allowing ratings from 0 (no symptoms) to 4 (severe symptoms) for each Parkinson's motor symptom. The Movement Disorders Society (MDS) commissioned a revision of the scale, resulting in a new version, termed the MDS sponsored UPDRS revision (MDS-UPDRS) (Goetz et al, 2008). In this study, the MDS-UPDRS version will be used.

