12.1 Statistical Analysis Overview

Due to the small sample size of this study, statistical analysis will be mainly exploratory and descriptive: t-tests (or Mann-Whitney u-tests if normality of the data is not met) are used to compare the difference of a continuous measure between groups (such as patient age at baseline, various efficacy measures), and contingency tables and chi-square tests are used to compare the difference of a categorical variable (such as patient gender at baseline, various safety and adverse events).

To minimize the potential confounding effects of gender and MOCA score on the treatment effect, we will use stratified block randomization when assigning patient to one of the four study groups. The stratification factors will be gender (male/female) and MOCA score (low <22/30 and high>23/30). We will use block size of four.

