12.3 Statistical Analysis of Second Aim – efficacy measures

For each of the efficacy outcome measures, we will report mean differences and 95% confidence intervals between Visit 2 (Baseline/Initial Treatment) and Visit 3 (Final Treatment/Safety) for each study group. In the event of an early withdrawal, measures taken at the early withdrawal visit will be used in

place of Visit 3 data, if possible. Possible trends in cognitive function, motor function, and mood and apathy scores will be addressed.

We will look at the individual components and domains assessed by the chosen cognitive, motor, mood, and apathy measures to determine if any appear to be more sensitive to IN insulin. We will also explore the data for components that have a larger dose response. That is, they increase or decrease as the dose-level increases.

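### UPDRS part III is scored twice before treatment, but Section 12.3 uses only the Visit 2 score: a missed efficiency for the motor endpoint, not an error

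*Combined protocol and SAP*

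**What the plan says.** The motor examination is scheduled three times. Section 7.1.1 (Visit 1) lists "Complete physical exam, including neurological exam with UPDRS part III". Section 7.1.2 (Visit 2) lists "Perform UPDRS III", ahead of randomization and the first in-clinic dose. Section 7.1.5 repeats it at Visit 3, and Table 3 marks all three visits. Section 7.4 fixes one instrument: "In this study, the MDS-UPDRS version will be used".

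On timing, Section 7.1.1 states "Visit 2 will be scheduled within 2 weeks" and Section 7.1.2 states "Visit 3 will be scheduled in 21 days", each with a window of 5 days either way. The opening text of Section 7 adds a qualification: "A recent office visit (within 3 months) may be used to replace a portion of the screening visit", provided the record holds what is needed to judge eligibility.

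On analysis, Section 12.3 gives one rule for every efficacy measure: mean differences with 95% confidence intervals "between Visit 2 (Baseline/Initial Treatment) and Visit 3 (Final Treatment/Safety) for each study group". For comparisons across arms, Section 12.1 says t-tests or Mann-Whitney tests "are used to compare the difference of a continuous measure between groups". No model with a baseline covariate is planned, and Section 12 does not mention the Visit 1 motor score.

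**The concern.** Both earlier scores precede study drug, and inclusion criterion 8 requires antiparkinsonian doses to be stable for at least a month before the baseline visit. On schedule, the two are about two weeks apart. The Visit 1 score therefore carries information about each participant's pre-treatment motor level, and the planned analysis leaves it out. The noise in the single Visit 2 score enters each change score in full.

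What is at stake is precision. Motor function is a secondary endpoint, the arms have 7, 7, 9 and 7 participants, and Section 12.4 says that the study looks for trends in the secondary outcomes. With no power target, the width of the intervals is the main thing that the efficacy analysis can improve, and the extra score needs no added visit or test.

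**Working it through.** **Inputs.** Visits fall at about weeks -2, 0 and 3 (Table 3). Arm sizes are 7 + 7 + 9 + 7 = 30 (Table 2). The documents give no SD or between-visit correlation for the motor score and no power figure (Section 12.4), so there is no planned number to reproduce. I assume the same SD, s, at each visit. The correlations r12, r13 and r23 between Visits 1, 2 and 3 are assumed and varied. I take the planned between-group comparison to be a comparison of change from Visit 2 to Visit 3.

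**1. Planned change score.** Var(Y3 - Y2) = 2s²(1 - r23). All ratios below are relative to this.

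**2. Change from the mean of Visits 1 and 2.** Var = s²[1 + (1 + r12)/2 - r13 - r23].
- Equal correlation r: 1.5s²(1 - r), so the ratio is 1.5/2 = 0.75 whatever r is.
- r12 = r23 = 0.85, r13 = 0.80: (1 + 0.925 - 0.80 - 0.85)/0.30 = 0.275/0.300 = 0.917.
- First-order decay, r13 = 0.85² = 0.7225: 0.3525/0.300 = 1.175, which is a loss.

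**3. Visit 3 score with Visit 2 and Visit 1 as separate covariates, all four arms in one model.** The residual variance is s²[1 - (r13² + r23² - 2·r12·r13·r23)/(1 - r12²)]. With equal r, its ratio to the planned variance is (1 + 2r)/[2(1 + r)]. Estimating k slopes from 30 - 4 = 26 within-arm degrees of freedom inflates the variance of an arm difference, on average under normality, by 25/(25 - k): 25/24 for one covariate and 25/23 for two.
- r = 0.8: 2.6/3.6 = 0.722; × 25/23 = 0.785.
- 0.85/0.85/0.80: 1 - 0.2065/0.2775 = 0.2559; /0.30 = 0.853; × 25/23 = 0.927.
- 0.85 with first-order decay: (1 - 0.7225)/0.30 = 0.925; × 25/23 = 1.005.

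For Visit 2 as the only covariate, the ratio is (1 + r23)/2 × 25/24.

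| Assumed r12 / r23 / r13 | Averaged baseline | Visit 2 covariate only | Visits 1 and 2 as covariates |
|---|---|---|---|
| 0.70 / 0.70 / 0.70 | 0.750 | 0.885 | 0.767 |
| 0.80 / 0.80 / 0.80 | 0.750 | 0.938 | 0.785 |
| 0.90 / 0.90 / 0.90 | 0.750 | 0.990 | 0.801 |
| 0.85 / 0.85 / 0.80 | 0.917 | 0.964 | 0.927 |
| 0.85 / 0.85 / 0.7225 | 1.175 | 0.964 | 1.005 |
| 0.90 / 0.90 / 0.81 | 1.200 | 0.990 | 1.033 |

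A simulation with arms of 7, 7, 9 and 7 agrees with the covariate columns to within 0.01. In the last two rows Visit 1 adds nothing once Visit 2 is known.

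**4. How much is due to Visit 1.** Part of the gain comes from adjusting for baseline at all. At equal r = 0.8, adding Visit 1 takes the ratio from 0.938 to 0.785, a further 16% (0.785/0.938 = 0.837). At 0.85/0.85/0.80 the further gain is 4% (0.927/0.964 = 0.962). If Visit 1 is uninformative, adding it costs 24/23 - 1 = 4% relative to Visit 2 alone.

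**5. An old office score.** Assume short-term reliability of 0.9, weekly decay of 0.995, 0.99 or 0.98, and a score taken at about week -13. The averaged baseline then has ratios of 0.90, 1.01 and 1.14.

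**The case against.** The strongest reply is that nothing is wrong. One pre-dose baseline, defined once for all efficacy measures, is valid and conventional. Sections 12.1 and 12.4 call the analysis mainly exploratory and descriptive, the primary aim is safety, and no decision depends on the width of a motor interval. That stands, and it limits the point to an efficiency gain.

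The second reply is that Visit 1 is not a matched replicate. Section 5 states the ON-state for the baseline UPDRS but not for the screening one. Visits 2 and 3 are fasting visits and Visit 1 is not. An office record up to three months old may replace part of screening, and the text does not say whether that includes the motor examination. A systematic difference between Visits 1 and 2 would bias a within-group change from their mean, and randomization protects only contrasts between arms. This defeats averaging as the main baseline. It does not defeat separate covariates: the data set the weight given to Visit 1, and the result is a between-arm contrast.

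Third, only the motor score has this second measurement on the same scale. The cognitive battery, mood and apathy scales have one pre-treatment score, at Visit 2. A more precise motor analysis would tilt the search for the most sensitive measure toward motor function. That also stands, and the fix allows for it.

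A reader might also infer that a two-score baseline reduces regression to the mean. The documents do not support that: no UPDRS part III threshold governs entry, and the Hoehn & Yahr limit is first applied at screening, so selection would affect Visit 1 at least as much as Visit 2.

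**Conclusion.** The point holds as a missed efficiency for the motor endpoint. A collected pre-treatment score goes unused, and a between-group model that uses it is likely to be more precise than the planned change score. Under the assumed correlations the variance is 7% to 23% lower, so standard errors are about 4% to 12% smaller (square roots of 0.927 and 0.767). If Visit 1 carries nothing beyond Visit 2, the variance is about 0.5% higher at an adjacent-visit correlation of 0.85 and 3% higher at 0.90. These figures assume equal variances, normality and a Visit 1 score for everyone; substituted office scores would shrink the gain.

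Two stronger readings are tempting. One is that Section 12.3 is in error, which it is not. The other is that the plan gives up a quarter of the variance. That 25% is an upper bound for a change score from an averaged baseline with exchangeable visits. With unequally spaced visits the same averaging could gain 8% or lose 18%, and the documents cannot say which.

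**What to change.** In Sections 12.1 and 12.3, before unblinding:

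- Compare motor outcome between groups with one linear model across all four arms. Use Visit 3 UPDRS part III as outcome (or the early-withdrawal value that 12.3 already allows), arm as factor, and the Visit 2 and Visit 1 scores as separate covariates.
- Where an office-visit score replaced the Visit 1 examination, treat the Visit 1 covariate as missing, for example with a constant value plus a missing indicator. The substitution is settled before randomization, so it cannot depend on arm.
- Keep the within-group Visit 2 to Visit 3 change and its interval as stated.
- Report change from the mean of Visits 1 and 2 only as a sensitivity analysis.
- For the question of which measures are most sensitive to insulin, compare measures on the common Visit 2 to Visit 3 change.

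The cost is SAP wording, with no change to visits or screening conduct. Beyond the planned change score, the model uses two degrees of freedom, or three with an indicator. Compared with a model using Visit 2 alone, that is one or two more. Residual degrees of freedom are 30 - 4 - 2 = 24, or 23 with an indicator. The remaining downside is a motor analysis that differs in form from that of the measures with a single pre-treatment score.

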
Primary Objectives:
 
 • To determine the safety and tolerability of three different doses of intranasal insulin in patients with Parkinson's disease (PD) 	

Secondary Objectives:
 
 • To evaluate efficacy of intranasal insulin on cognitive functioning in PD • To evaluate efficacy of intranasal insulin on motor function in PD • To evaluate efficacy of intranasal insulin on mood and apathy in PD • To identify which outcome measures are most sensitive to effects of intranasal insulin in PD 	
STUDY DESIGN	
Study Type	Dose-finding
Control Type	None
Study Indication Type	Dose-finding, safety
Blinding Schema	Double blinded
Device	SipNose nasal device
Study Design	randomized, parallel-group, double blind, placebo-controlled
Planned Duration of Subject Participation	8 weeks (Treatment duration: 3 weeks)
PRIMARY ENDPOINTS	

 • Composite safety event of either: a reduction of fasting glucose to <70 mg/dL or an unintended reduction of weight >5% • Pre-post change in safety measures (fasting glucose and weight) • Number of AEs and SAEs 	
SECONDARY ENDPOINTS	

 • Pre-post change in cognitive function measures 	

 • Pre-post change in motor function measures • Pre-post change in mood and apathy measures 	
INVESTIGATIONAL PRODUCTS, DOSE AND MODE OF ADMINISTRATION	
Investigational Product	
Regular insulin (Novolin-R) in 3 different doses and placebo
 
Dose 1, group with 7 participants: 20 IU/IN (10 units IN in one nostril twice daily x 21 days, volume 100 µl)
 
Dose 2, group with 7 participants : 40 IU/IN (10 units IN in each nostril twice daily x 21 days, volume 100 µl)
 
Dose 3, group with 9 participants: 80 IU/IN (20 units IN in each nostril twice daily x 21 days, volume 200 µl)
 
Dose 4, group with 7 participants: placebo (each nostril, twice daily)

SUBJECT SELECTION	
Targeted Accrual	30 subjects. We estimate a need to consent 50 participants in order to reach this goal.
INCLUSION CRITERIA	

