3.2 Secondary Objectives

- To evaluate efficacy of intranasal insulin on cognitive functioning in PD
- To evaluate efficacy of intranasal insulin on motor function in PD
- To evaluate efficacy of intranasal insulin on mood and apathy in PD

To identify which outcome measures are most sensitive to effects of intranasal insulin in PD

4 Endpoint(s)

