12.4 Statistical Power

As stated above, due to the sample size limitation of this study, no particular statistical power is under consideration during the study design phase with the intent to detect a meaningful clinically significant difference between study groups for any of the primary or secondary outcome measures; statistical analysis of this study will be mainly exploratory and descriptive.

The overall goal of the study is to identify a safe dose intranasal insulin with trends towards the secondary outcomes. Three different doses (and placebo) will be used, with the highest number of subjects (9) in the group with the highest dose, a model previously used by Finger et al. (2014).

13 Study Conduct Considerations

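### Section 12.3 describes a dose response by direction only, with no trend estimate or interval; a slope on dose with a 95% CI would serve the sensitivity objective better from the same data

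*Combined protocol and SAP*

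**What the plan says.** Section 3.2 lists as a secondary objective "To identify which outcome measures are most sensitive to effects of intranasal insulin in PD". Section 12.3 serves it in two sentences. The first looks across the components and domains of the cognitive, motor, mood and apathy measures "to determine if any appear to be more sensitive to IN insulin". The second says "We will also explore the data for components that have a larger dose response", and the only explanation that follows is that "they increase or decrease as the dose-level increases".

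The estimates promised in 12.3 are Visit 2 to Visit 3 mean changes with 95% confidence intervals within each study group. Section 12.1 allows t-tests or Mann-Whitney tests between groups for efficacy measures, but names no arm pairs or significance level and does not connect them to the dose-response screen. Sections 12.1 and 12.4 call the analysis mainly exploratory and descriptive, and 12.4 sets no power target. Section 12.4 also gives the overall goal as to "identify a safe dose intranasal insulin with trends towards the secondary outcomes", so the trends are meant to be used.

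**The concern.** A direction across dose levels is not an estimate. It carries no size, no precision and no allowance for the number of scores inspected. With arms of 7 to 9 people, the arm means will often line up by chance, and a real effect will often fail to line up because one small arm is out of place.

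The measures named here are natural candidates for outcomes in a later trial, and the same trends inform the stated goal in 12.4. If the screen is run on direction, the list of sensitive measures may be largely chance, and information about dose already present in the 30 participants goes unused.

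**Working it through.** The documents give no power, SD, effect size or significance level for this analysis, so there is no figure to reproduce. Effect sizes and correlations below are assumptions, shown over a range. Errors are taken as normal with a common SD of change.

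**Inputs**
- Arm sizes (Table 2): placebo 7, 20 IU 7, 40 IU 7, 80 IU 9; 7 + 7 + 7 + 9 = 30.
- Scores (counted from sections 7.4 and 7.5, not stated by the plan): MoCA 1, Digit Span 3, Trailmaking 2, Line Orientation 1, Logical Memory 3, Hopkins 3, Brief Visuospatial 3, Stroop 3, letter fluency 1, category fluency 1, MDS-UPDRS III 1, Beck 1, Apathy 1 = 24. Table 3 has no MoCA at Visit 2, so a Visit 2 to 3 change exists for 23.
- Reading: the four arm means of change, with placebo as dose 0, are ordered upward or downward.

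**Step 1. Chance ordering of one score.** With equal arms, 2 of the 4! = 24 possible orders are monotone: 2/24 = 8.3%. With 7/7/7/9, simulation (2,000,000 draws) gives 7.8%. With one participant lost per arm it is 7.7%.

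**Step 2. Chance orderings over all scores.** Expected number = k × 0.078: 24 × 0.078 = 1.9; 23 × 0.078 = 1.8. If the scores are independent, P(at least one of 24) = 1 − (1 − 0.078)^24 = 86%. By simulation it is 81%, 72% and 59% at inter-score correlations of 0.3, 0.5 and 0.7; the expected number does not change. With only the 13 whole-test scores, 1.0 is expected, and at least one occurs 65% of the time if they are independent.

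**Step 3. Detecting a real effect.** Let D be the placebo-to-80 IU difference in SD units, linear in dose. The comparator is the slope on dose, tested at the same 7.8% per-score false-positive rate.

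| D (SD) | Ordered in the right direction | Slope test, unadjusted, same error rate |
|---|---|---|
| 0.5 | 14% | 23% |
| 0.8 | 23% | 45% |
| 1.0 | 30% | 61% |
| 1.5 | 48% | 90% |

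The advantage at 1 SD does not depend on exact linearity: 28% v 55% if the effect plateaus from 40 IU, 15% v 41% if all three doses act equally, 16% v 66% if only 80 IU acts. Neither method handles an effect that peaks at 20 IU and returns to zero at 80 IU (under 1% ordered in either direction; 15% for the slope).

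**Step 4. Precision of the slope.** Code dose as x = 0, 0.25, 0.5, 1 (units of 80 IU).
- Mean x = (7×0 + 7×0.25 + 7×0.5 + 9×1)/30 = 0.475.
- Sum of squares = 7×0.475² + 7×0.225² + 7×0.025² + 9×0.525² = 4.42.
- SE of slope = 1/√4.42 = 0.476 SD.
- 95% half-width = 2.05 × 0.476 = 0.97, about 1 SD per 80 IU.

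For comparison, the within-arm intervals that 12.3 already promises have half-widths of 0.92 SD (n = 7) and 0.77 SD (n = 9), and they do not estimate a trend.

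**Step 5. What adjustment would do.** Using the slope at 0.05 unadjusted, 24 × 0.05 = 1.2 false positives are expected (23 × 0.05 = 1.15). Bonferroni at 0.05/24 detects about 12% of 1 SD effects. A max-T adjustment at 5% family-wise detects about 13% to 19% over correlations 0 to 0.7. Both are below the 30% of the ordering rule.

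**The case against.** The strongest reply is that the plan says openly that it is exploratory and unpowered, and that 12.3 speaks of exploring and of possible trends. That stands, and it limits the weight of the point. It does not supply a summary for a listed objective, and a slope with an interval is itself a descriptive summary.

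A second reply is that the ordering rule is a construction. This also stands in part. Section 12.3 mentions neither means nor a strict order, does not say that placebo counts as a dose level, and sets no pass or fail decision. Speaking of a larger response also hints at size. A reader might infer that the plan fixes a formal ordering test; the text does not go that far. The calculation shows what the only written explanation implies if applied literally. Ordering just the three insulin doses would give about 32% by chance per score, or 24 × 0.322 = 7.7 scores.

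Third, 12.3 gives confidence intervals and 12.1 gives between-group tests, so sampling error is not ignored in the efficacy analysis as a whole. That is correct, but neither is tied to the dose-response screen.

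A reader might also infer that the remedy is to name a measure only after strict multiplicity control, and that this would achieve the 61% detection. Neither follows. The 61% belongs to an unadjusted slope, and Step 5 shows that an adjusted gate would miss more 1 SD effects than ordering does. In a declared exploratory study of 30 people, strict error control is a trade-off, not a requirement.

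**Conclusion.** The concern holds as a limited one. Section 12.3 offers direction across doses as its only account of a dose response, and no trend estimate or interval supports the secondary objective on sensitive measures. Read as ordering of four arm means, this gives 1.8 to 1.9 chance dose responses among 23 to 24 scores. For a linear 1 SD effect it detects about half as often as a slope with the same per-score error rate (30% v 61%).

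It would be too strong to say that the trial will almost always name a false measure. The chance of at least one ordered score among 24 is about 59% to 86%, depending on a correlation the documents do not give, and lower again if only whole-test scores are screened. The results rest on the assumed effect sizes and correlations, normal errors, a common SD and the score count above. The slope improves ranking and makes uncertainty visible; it does not remove the limits of 30 participants. The primary safety aim is unaffected.

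**What to change.** In 12.3, replace the direction criterion with the following:
- For each score, estimate the slope of Visit 2 to Visit 3 change on assigned daily dose (0, 20, 40, 80 IU) over all randomised participants. Standardise the scores and align their signs so that a positive slope always means improvement. Give the 95% CI, expected half-width about 1 SD per 80 IU.
- Show the four arm means beside each slope, so that a non-linear pattern is visible.
- Rank measures by the slope. State in advance the list and number of scores screened, including how MoCA is handled without a Visit 2 value, and how many would be expected to stand out by chance (about 1.2 of 24 with a 95% CI excluding zero).
- Label these results, and the trends in 12.4, hypothesis-generating.
- A max-T permutation result may be added as a supplement, but should not decide which measures are named. If labels are permuted within strata, 12.1 must first say where MoCA scores of 22 and 23 belong, since the stated low (<22) and high (>23) groups leave them out.

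The cost is SAP wording and a short program before unblinding; no new data or visits are needed. The downsides are that the slope assumes a roughly linear shape and that fewer measures may look convincing.
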